8 SAFETY AND ADVERSE EVENTS

8.1 Definitions

8.1.1 Unanticipated Problems Involving Risk to Subjects or Others

Any incident, experience, or outcome that meets all of the following criteria:

- Unexpected in nature, severity, or frequency (ie, not described in study-related documents such as the Institutional Review Board (IRB)-approved protocol or consent form, the IB, etc)
- Related or possibly related to participation in the research (ie, possibly related means there is a reasonable possibility that the incident experience, or outcome may have been caused by the procedures involved in the research)
- Suggests that the research places subjects or others at greater risk of harm (including physical, psychological, economic, or social harm).

8.1.2 Adverse Event

An AE is any symptom, sign, illness, or experience that develops or worsens in severity during the course of the study. Intercurrent illnesses or injuries should be regarded as AEs. Abnormal results of diagnostic procedures are considered to be AEs if the abnormality:

- results in study withdrawal
- is associated with an SAE
- is associated with clinical signs or symptoms
- leads to additional treatment or to further diagnostic tests
- is considered by the investigator to be of clinical significance

For this protocol, untoward medical occurrences that should be reported as AEs include the following:

- All AEs that are suspected or are not suspected to be due to study drug.
- Overdose (administration of a study drug dose > 4 times the highest intended total daily dose level for this protocol [> 160 mg/kg/day]) of study drug.
- All reactions from medication misuse, abuse, withdrawal, sensitivity, or toxicity.
- All reactions that result from medication errors or uses of the study drug outside what is described in the protocol.
- Apparently unrelated illnesses, including the worsening of a preexisting illness.
- Injury or accidents. Note that if a medical condition is known to have caused the injury or accident (a fall secondary to dizziness), the medical condition (dizziness) and the accident (fall) should be reported as 2 separate AEs. The outcome of the accident (hip fracture secondary to the fall) should be recorded in source documents.

- Abnormalities in physiological testing or physical examination findings that require clinical intervention or further investigation (beyond ordering a repeat [confirmatory] test).
- A pre-existing condition (eg, allergic rhinitis) must be noted on the appropriate CRF for Visit 1, but should not be reported as an AE unless the condition worsens or episodes increase in frequency during the AE reporting period. Diagnostic and therapeutic non-invasive and invasive procedures, such as surgery, should not be reported as AEs. However, the medical condition for which the procedure was performed should be reported if it meets the definition of an AE. For example, an acute appendicitis that begins during the AE reporting period should be reported as the AE and the resulting appendectomy should be recorded in the source documents. If a surgical procedure was planned prior to entry into the study, and the surgery is not performed because of a worsening of a baseline condition, this should not be reported as an AE. Note that, as described in the SAE paragraph below, any inpatient hospitalization occurring as the consequence of an AE during the study period should be reported as an SAE.

Each AE is to be classified as serious or non-serious by the investigator using medical and scientific judgment.

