3.1 Inclusion Criteria

Subjects who will be selected for this study must meet the following criteria:

1. Age \geq 2 years old and \leq 12 years old, male or female, at Week 0 (at time informed consent/assent is signed)
2. Documentation of a diagnosis of Dravet syndrome or CDKL5 deficiency resulting from a nonsense mutation in 1 allele, as evidenced by medical records, genetic testing, and the following clinical feature:
 - a. Failure to control seizures despite appropriate trial of 2 or more AEDs at therapeutic doses
3. Between 1 to 3 baseline AEDs at stable doses for a minimum of 4 weeks prior to enrollment (ie, Screening visit)
 - a. Vagus nerve stimulator (VNS), ketogenic diet, and modified Atkins diet do not count towards this limit but must be unchanged for 3 months prior to enrollment (Screening).
4. VNS must be on stable settings for a minimum of 3 months prior to the Baseline visit
5. If on ketogenic or modified Atkins diet, must be on stable ratio for a minimum of 3 months prior to the Baseline visit
6. Written consent obtained from the subject or subject's legal representative must be obtained prior to performing any study procedures
7. Minimum of 6 convulsive or drop seizures with duration $>$ 3 seconds over the 4 weeks of diary screening prior to randomization and \geq 6 convulsive or drop seizures with duration $>$ 3 seconds during the 4 weeks from Screening to Baseline.

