7.6.1 Adverse Events

Summary information (the number and percent of subjects by treatment) will be tabulated for:

- TEAEs, including clinical and laboratory AEs

- Treatment-related AEs
- TEAEs by severity
- Treatment-related AEs by severity
- SAEs
- AEs leading to discontinuation

Summaries will be presented by treatment groups and categorized by System Organ Class and Preferred Term. The frequencies of AEs displayed will be the crude rates that represent the number of subjects experiencing AEs divided by the total number of subjects.

It should be noted that all laboratory data sent to and analyzed by the NYU laboratory will be reported to the investigator. However, only those laboratory abnormalities meeting the protocol-defined criteria of an AE (ie, those that require clinical intervention or further investigation beyond ordering a repeat [confirmatory] test) should be reported as AEs in the appropriate CRF, whether they were analyzed by the NYU laboratory or another laboratory.

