8.4 Recording of Adverse Events

At each contact with the subject, the investigator will seek information on AEs by specific questioning and, as appropriate, by examination. Information on all AEs will be recorded immediately in the source document, and also in the appropriate AE module of the CRF. All clearly related signs, symptoms, and abnormal diagnostic procedures results will be recorded in the source document, but should be grouped under one diagnosis whenever possible.

All AEs occurring during the study period will be recorded. The clinical course of each event will be followed until resolution, stabilization, or until it has been determined that the study drug or participation is not the cause. Serious adverse events that are still ongoing at the end of the study period will be followed up to determine the final outcome. Any SAE that occurs after the study period and is considered to be possibly related to the study drug or study participation will be recorded and reported immediately.

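### Section 8.1.2 calls injuries adverse events, but its worked example sends the injury from a fall to source documents, so fractures and head injuries may be under-counted in the AE tables

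*Combined protocol and SAP*

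**What the plan says.** All references are to the combined protocol and SAP.

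- **General rule, Section 8.1.2.** "Intercurrent illnesses or injuries should be regarded as AEs". Injuries and accidents also appear in the list of occurrences to be reported.
- **Worked example, same bullet.** Where a medical condition is known to have caused the event, "the medical condition (dizziness) and the accident (fall) should be reported as 2 separate AEs". The next sentence reads: "The outcome of the accident (hip fracture secondary to the fall) should be recorded in source documents".
- **Parallel example, later in Section 8.1.2.** Acute appendicitis arising in the reporting period "should be reported as the AE and the resulting appendectomy should be recorded in the source documents".
- **Recording, Section 8.4.** "Information on all AEs will be recorded immediately in the source document, and also in the appropriate AE module of the CRF".
- **Tabulation, Section 7.6.1.** "Summaries will be presented by treatment groups and categorized by System Organ Class and Preferred Term". Separate tables by severity are planned. Frequencies are numbers of subjects with an event divided by all subjects.
- **Population, Section 3.1.** Entry requires "Minimum of 6 convulsive or drop seizures with duration" above 3 seconds over the four diary weeks. Section 2.2.1 counts drop attacks in the primary endpoint.

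**The concern.** The general rule and the worked example give different answers for the same event, and nothing says which prevails. Site staff deciding what to enter are likely to follow the specific example.

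Children with drop seizures fall, and what matters clinically is whether a fall caused a bruise, a fracture or a head injury. Such injuries could become more or less frequent on ataluren than on placebo. If the AE module holds only the fall, the tables cannot show that difference, and any severity grade attaches to the fall and not to the injury. Characterizing safety is a secondary objective in Section 2.1, and Section 7.1 describes it as the primary one, so the injury terms bear on a stated aim of the trial.

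**Working it through.** The plan states no figure on this point, so the check is a comparison of rules.

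**Step 1: does the example exclude the fracture from the AE module?** The word *only* does not appear, so this has to be inferred. Three features point to exclusion.

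1. The example counts two AEs, the condition and the accident. The fracture is a third item and is handled differently.
2. The appendicitis example draws the same contrast between reporting as an AE and recording in source. Section 8.1.2 says there that procedures are not reported as AEs, so in that example the source-document phrase marks something that is not an AE.
3. Section 8.4 already sends every AE to both the source document and the CRF. If the fracture were an AE, a sentence sending it to source documents would add nothing.

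Exclusion is therefore the natural reading of the example, though not an explicit one.

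**Step 2: do other rules include it?** Several point that way.

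- The general rule on injuries, quoted above.
- A further bullet in Section 8.1.2 makes these reportable: "Abnormalities in physiological testing or physical examination findings that require clinical intervention or further investigation", beyond a confirmatory repeat test. A fracture needing treatment fits.
- Section 8.1.2 also treats an abnormal diagnostic result as an AE if it leads to treatment or further tests.
- Section 8.3 makes a condition responsible for surgery an AE if it meets the AE criteria. Whether the fracture meets them is the point in dispute.

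None of these says that it overrides the worked example.

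**Step 3: trace a fracture after a fall.**

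- *Site follows the worked example:* the fall, and the cause if it is itself an AE, enter the tables. The fracture has no Preferred Term row and no grade.
- *Site follows the general rule:* the fracture is an AE and is tabulated.
- *Child is admitted:* the event is a serious AE on either reading (Sections 8.1.2, 8.1.3 and 8.3), but the documents do not say which term is coded.

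**Step 4: apply it to this population.** The printed example is dizziness, so extending it to drop seizures is an inference. Under Sections 8.1.2 and 8.2.1 a preexisting condition is an AE only if it worsens. After a seizure within a child's usual pattern, the fall could therefore be the only term entered.

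**Step 5: how many subjects need checking?** Section 7.1 reports 7 and 8 subjects randomized and enrolment stopped. It labels both groups as Dravet syndrome. Assuming that they are separate groups, 7 + 8 = 15.

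**The case against.** The strongest reply is that the plan, read as a whole, already makes a significant injury reportable. Recording in source does not forbid CRF entry, and Section 8.4 requires both for an AE. The rules in Step 2 cover most injuries needing care. Section 2.2.1 collects emergency room visits and hospitalizations, and Section 7.7 tabulates them per 28 days by treatment group. Where a serious event is reported as a narrative, Section 8.5.1 requires a description. AE summaries are descriptive, with no tests (Section 7.6), and the trial is small and at one center. Reporting cause and accident as AEs and keeping the consequence in source is also a recognizable convention.

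Much of this stands, and it limits the finding. It does not remove the conflict. The visit counts do not identify injuries, and an injury treated without admission may leave no injury term in any AE table. Nor does the lack of testing help, because descriptive tables depend on what was entered.

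A reader might infer two stronger conclusions. The first is that seizure-related fractures and head injuries are recorded in source documents only and are lost from the AE tables. The text does not say *only*, other rules favor entry, and falls and serious events remain visible.

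The second is that the loss can be counted. At the entry minimum, 6 × 3 = 18 qualifying seizures per child per 12 weeks, 18 × 15 = 270 per period, and 540 over two periods. One could multiply this by an assumed injury rate. The documents give no such rate. The 540 counts all qualifying seizures and not falls, and it assumes that the entry minimum continues. Section 1.1.1 says that many children with CDKL5 never walk independently. Section 7.6.1 counts subjects and not events. No number of missing injuries follows.

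**Conclusion.** The point holds as an internal inconsistency in Section 8.1.2 that could lead sites to code injuries from accidents differently and so under-count them by Preferred Term and severity. The direction is toward under-counting. The size cannot be estimated from the documents and may be zero if the site has been entering injuries under the general rule.

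The conclusion rests on two inferences: that the worked example is read as excluding the injury from the AE module, and that it is applied to falls from seizures. Both are reasonable readings, but neither is stated. The correction is worth making because it is cheap and the harm is a foreseeable one in this population.

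**What to change.** Replace the last sentence of the injury bullet in Section 8.1.2 with wording such as: *The injury resulting from the accident (for example a fracture, head injury or laceration) is also entered in the CRF AE module, with its own severity and seriousness, and is linked to the accident and to the condition that caused it.*

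Before database lock, and ideally while treatment assignments are still masked, check source documents for the roughly 15 randomized subjects, over all periods that Section 7.6 summarizes, and enter any injury recorded only there.

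The cost is one sentence, a short source review at a single center and a few more AE entries. Where the fall is already entered, the number of subjects with any AE does not change. What changes is the injury rows and, where the injury is graded worse than the fall, the severity tables.

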8.1.3 Serious Adverse Event

Adverse events are classified as serious or non-serious. A *serious adverse event* is any AE that is:

- fatal
- life-threatening
- requires or prolongs hospital stay
- results in persistent or significant disability or incapacity
- a congenital anomaly or birth defect
- an important medical event

Important medical events are those that may not be immediately life threatening, but are clearly of major clinical significance. They may jeopardize the subject, and may require intervention to prevent one of the other serious outcomes noted above. For example, study drug or other drug overdose or abuse, a seizure that did not result in inpatient hospitalization, or intensive treatment of bronchospasm in an emergency department would typically be considered serious.

Overdose of study drug is considered to be administration of a study drug dose > 4 times the intended total daily dose level for this protocol (> 160 mg/kg/day).

All AEs that do not meet any of the criteria for serious should be regarded as non-serious AEs.

Note that any SAEs occurring within 4 weeks of the date of last dose should be reported to the investigator who will notify PTC Therapeutics.

8.2 Adverse Event Reporting Period

The study period during which AEs must be reported is defined as the period from the initiation of any study procedures (ie, after informed consent is given) to the end of the study drug follow-up. For this study, the study drug follow-up is defined as 4 weeks following the final administration of study drug.

8.2.1 Preexisting Condition

A preexisting condition is one that is present at the start of the study. A preexisting condition should be recorded as an AE if the frequency, intensity, or the character of the condition worsens during the study period.

8.2.1.1 General Physical Examination Findings

At screening, any clinically significant abnormality should be recorded as a preexisting condition. At the EOS Visit, any new clinically significant findings/abnormalities that meet the definition of an AE will also be recorded and documented as an AE.

8.2.2 Post-study Adverse Event

All unresolved AEs will be followed by the Investigator until the events are resolved, the patient is lost to follow-up, or the AE is otherwise explained. At the last scheduled visit, the investigator will instruct each subject to report any subsequent event(s) that the subject, or the subject's personal physician, believes might reasonably be related to participation in this study. The investigator will notify PTC Therapeutics of any death or AE occurring at any time after a subject has discontinued or terminated study participation that may reasonably be related to this study. The investigator will notify PTC Therapeutics if he becomes aware of the development of cancer or of a congenital anomaly in a subsequently conceived offspring of a subject that has participated in this study.

8.2.3 Abnormal Laboratory Values

A clinical laboratory abnormality will be documented as an AE if any one of the following conditions is met:

- The laboratory abnormality is not otherwise refuted by a repeat test to confirm the abnormality.
- The abnormality suggests a disease and/or organ toxicity.
- The abnormality is of a degree that requires active management: change of dose, study drug discontinuation, more frequent follow-up assessments, further diagnostic investigation, etc.

8.3 Hospitalization, Prolonged Hospitalization or Surgery

Any AE that results in hospitalization or prolonged hospitalization will be documented and reported as an SAE unless specifically instructed otherwise in this protocol. Any condition

responsible for surgery will be documented as an AE if the condition meets the criteria for an AE.

Neither the condition, hospitalization, prolonged hospitalization, nor surgery are reported as an AE in the following circumstances:

- Hospitalization or prolonged hospitalization for diagnostic or elective surgical procedures for a preexisting condition. Surgery should **not** be reported as an outcome of an AE if the purpose of the surgery was elective or diagnostic and the outcome was uneventful.
- Hospitalization or prolonged hospitalization required to allow efficacy measurement for the study.
- Hospitalization or prolonged hospitalization for therapy of the target disease of the study, unless it is a worsening or increase in frequency of hospital admissions as judged by the clinical investigator.

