1.1.2 Dravet Syndrome

Sodium channel, voltage-gated type 1 alpha (*SCN1A* or Nav1.1) is the sodium channel $\alpha 1$ subunit gene and is expressed almost exclusively in the brain. Mutations in *SCN1A* can cause a variety of epilepsies that range from benign febrile seizures to severe epileptic encephalopathy and Dravet syndrome (Severe Myoclonic Epilepsy of Infancy; [Mulley 2005](#), [Catterall 2010](#)). The major mechanism underlying epilepsy appears to be impairment of gamma-aminobutyric acid interneuron inhibitory function ([Catterall 2005](#), [Yu 2006](#)).

Dravet syndrome was initially described in 1978 as Severe Myoclonic Epilepsy of Infancy by Charlotte Dravet ([Dravet 2011](#)). The incidence of Dravet syndrome is ~1 in 15,700 live births, comprising approximately 6% of epilepsies starting before the age of 3 years ([Hurst 1990](#), [Yakoub 1992](#), [Wu 2015](#)). It causes febrile and afebrile, generalized and unilateral, clonic or tonic-clonic seizures; it can also cause absence, absence-myoclonic, and complex partial seizures. Seizures typically begin in the first year of life in an otherwise normal infant. Initial seizures are often febrile status epilepticus ([Dravet 2005](#)). Later, myoclonic, atypical absence, and partial seizures often develop. Seizures are usually drug-resistant but the severity of the epilepsy tends to diminish around puberty. Developmental delays in the second year of life and intellectual disability are present in more than 95% of patients ([Chieffo 2011](#)). Autism spectrum disorder is diagnosed in approximately 25% of patients ([Genton 2011](#)). Most patients develop cerebellar dysfunction in later childhood, manifesting as an ataxic gait disorder, dysarthria, and intention tremor ([Genton 2011](#)). The mortality rate is high; approximately 15% of patients die by adolescence and 20% die by early adulthood ([Genton 2011](#)). SUDEP and status epilepticus are the most common causes of death.

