9.5 Records Retention

It is the investigator’s responsibility to retain essential study documents for at least 2 years after the last approval of a marketing application in their country and until there are no pending or contemplated marketing applications in their country or at least 2 years have elapsed since the formal discontinuation of clinical development of the investigational product.

10 Data Safety Monitoring Plan

A Safety Project Plan will be provided by PTC Therapeutics Pharmacovigilance outlining safety activities, processes, and study responsibilities. The PTC Therapeutics Pharmacovigilance Safety Lead-Pharmacist and Pharmacovigilance Safety Physician will be responsible for monitoring all SAEs, requesting follow-up information, and performing reconciliation.

The overall safety and conduct of the study will be monitored by the Principal Investigator, [name], the PTC Pharmacovigilance Safety Lead, and the PTC Pharmacovigilance Safety Physician. Under the safety monitoring plan, all SAEs will be reviewed. Data monitoring reviews will take place quarterly. Summary reports of the data monitoring review will also be taken quarterly.

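### A life-threatening seizure admission judged usual for the child can fall outside AE, and therefore SAE, reporting when 8.3 is read with 8.1.2, 8.1.3 and 8.2.1

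*Combined protocol and SAP*

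**What the plan says.** Section 8.3 starts from a general rule: "Any AE that results in hospitalization or prolonged hospitalization will be documented and reported as an SAE unless specifically instructed otherwise in this protocol". It then does instruct otherwise for three kinds of stay, under the lead-in "Neither the condition, hospitalization, prolonged hospitalization, nor surgery are reported as an AE in the following circumstances". The third kind is admission to treat the target disease: "Hospitalization or prolonged hospitalization for therapy of the target disease of the study, unless it is a worsening". The exception in full runs "unless it is a worsening or increase in frequency of hospital admissions as judged by the clinical investigator".

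Section 8.1.3 defines a serious adverse event from within the class of AEs: it "is any AE that is" fatal, life-threatening, leads to or prolongs a hospital stay, and so on. Among its examples of important medical events that would typically count as serious is "a seizure that did not result in inpatient hospitalization".

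Two other sections bear on the point. Section 8.1.2 says a pre-existing condition noted at Visit 1 is not an AE unless it worsens or its episodes become more frequent. It also makes any admission that follows an AE an SAE, with no exception for the target disease. Section 8.2.1 records a pre-existing condition as an AE if its frequency, intensity or character worsens.

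Section 1.1.2 says of Dravet syndrome that "SUDEP and status epilepticus are the most common causes of death". Section 10 says "Under the safety monitoring plan, all SAEs will be reviewed".

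**The concern.** The exemption in 8.3 reaches the seizure event itself, not only the hospital stay, and nothing in 8.3 brings back an event that is serious for a different reason, such as being life-threatening. What returns an event to reporting is the investigator's judgement that it is a worsening or an increase, and 8.3 gives no reference for that judgement.

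Three safeguards rest on the classification: the 24-hour SAE report to the drug supplier (8.5.2.1), the AE and SAE summaries by treatment (7.6 and 7.6.1), and the SAE review (Section 10). Section 3.6.1 lists seizure exacerbation as a possible reason to stop study drug. If grave seizure events are assessed one child at a time and each is called usual, a pattern across children or between treatments could be absent from the tables meant to show it.

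**Working it through.** No figure in the plan bears on this point, so the check sets the sections side by side.

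**Step 1. Is the event an AE?** Take a child with a seizure history who is admitted with life-threatening status epilepticus. The investigator considers this neither a worsening nor an increase in admissions. Under 8.3, neither the stay nor the condition is reported as an AE. Under 8.1.2 and 8.2.1, a pre-existing condition that has not worsened is not an AE either. The exclusion therefore has two sources, and an edit to 8.3 alone would leave the second in place.

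**Step 2. Can it still be an SAE?** In 8.1.3 the seriousness criteria apply to AEs. An event that is not an AE never reaches the life-threatening criterion. The admission rule in 8.1.2 does not help, because it applies only to an admission that follows an AE.

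**Step 3. Compare the four cases.**

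| Judged a worsening or increase? | Admitted? | Status under the text |
|---|---|---|
| Yes | No | AE (8.1.2, 8.2.1); typically serious by the example in 8.1.3 |
| Yes | Yes | AE and SAE (8.3, general rule) |
| No | No | Not an AE (8.1.2, 8.2.1) |
| No | Yes | Not an AE (8.3, 8.1.2, 8.2.1), so not an SAE even if life-threatening |

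The last row is the gap.

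**Step 4. How far does the seizure example in 8.1.3 reach?** Inclusion criterion 7 requires at least 6 convulsive or drop seizures in 4 weeks. At that floor, a child has 6 × (12 / 4) × 2 = 36 such seizures over the two 12-week treatment periods. The documents do not say which of these the example is meant to cover. It sits awkwardly beside the last row of the table but does not settle the matter.

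**Step 5. Is there a reference for worsening?** Section 7.4.1 defines baseline seizures and hospitalizations over the 4-week Screening Period, and 6.1.1.1 collects medical history at Visit 1. Section 8.3 refers to neither, and they can give opposite answers. For a child with no admission in those 4 weeks, any later admission is an increase on the screening count, yet it may be ordinary against a longer history.

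**Step 6. What still captures the event?** Section 2.2.1 collects status epilepticus episodes and emergency room visits or hospitalizations at Baseline and at each 6-week visit. Section 7.7 tabulates emergency room visits and hospitalizations as a single item. Status epilepticus is not in that list, although the opening sentence of 7.7 promises a summary of all efficacy endpoints.

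**The case against.** The strongest reply is that the carve-out already covers the harm that matters. A drug-related excess of severe seizures is by nature a worsening or an increase, so 8.3, 8.1.2 and 8.2.1 all return it to AE reporting. Investigator judgement is a deliberate choice in a population with frequent seizures. This stands for any excess that is recognised in the individual child. It does not cover an excess that shows only when cases are pooled, and it leaves a life-threatening event to a judgement with no stated reference.

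Second, SAE status is not the only route to review. Section 8.5.2.1 also requires 24-hour reporting of unanticipated problems, 8.5 sets a minimum for events that are related, unexpected, or serious or risky, 8.5.5 covers certain study events for the FDA, and Section 10 provides quarterly data monitoring. This stands in part. Unanticipated problems (8.1.1) and the FDA route for fatal or life-threatening events (8.5.5) both need an unexpected event, and an episode judged usual for the child may not qualify.

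Third, a reader might infer that 8.3 reverses the order of seriousness, so that a seizure without admission is serious while one with admission is not. The documents do not support that as a general rule. The example in 8.1.3 is qualified as typical and presupposes an AE. Compared like with like, a worsened seizure that leads to admission is both an AE and an SAE.

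**Conclusion.** The point holds in a limited form. An admission for the target disease that is life-threatening, but judged neither a worsening nor an increase, can be neither AE nor SAE under 8.3 together with 8.1.2 and 8.2.1. That conflicts with the life-threatening criterion in 8.1.3. A fatal event would probably be judged a worsening, so life-threatening status epilepticus is the realistic case.

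Three stronger readings should be set aside:

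- **Every target-disease admission drops out of reporting.** It does not; the exception for worsening or increase keeps many in.
- **The events are lost to the trial.** They are not; they are collected as endpoint data. What can be lost is their place in the SAE report, the AE and SAE tables and the SAE review.
- **A number of missed admissions can be stated.** It cannot; the documents give no admission rate, and any count would rest on an assumed one.

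The conclusion rests on a literal reading of the lead-in in 8.3 and of the SAE definition, and on the investigator calling the episode usual. It warrants a change because the rule, followed as written, can give a wrong result and the correction is cheap. Enrolment has stopped (7.1), but the plan includes a 96-week extension and the documents do not say that it has ended.

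**What to change.** Reconcile 8.1.2, 8.1.3, 8.2.1 and 8.3 with one statement that applies to all four. Suggested wording:

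*Neither the target-disease exemption in 8.3 nor the pre-existing-condition rule in 8.1.2 and 8.2.1 applies to an event that is fatal or life-threatening under 8.1.3. Such an event is recorded as an AE and reported as an SAE.*

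Then:

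1. State in 8.3 that a worsening or increase is judged against the child's seizure and admission history recorded at Screening.
2. List the target-disease admissions that remain exempt, by treatment period, in the safety listings.

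The change should not make every convulsion longer than 10 minutes an SAE. Section 7.4.1 defines status epilepticus by that duration alone, so an automatic rule would also take in episodes that were neither life-threatening nor admitted, at a reporting cost the documents give no means to estimate.

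The cost is a short amendment, a few more SAE reports and one listing. The change concerns reporting only and leaves the treatment of the child untouched.
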